4.7.1.1. Qualitative analysis

Values of the marker will be expressed in class, according to the limits of quantification (Below Lower Limit, In Range, Above Upper Limit). The percentage of values of the marker in each class will be described overall.

If the out-of-range percentage (Below Lower Limit or Above Upper Limit) is above 30% then the quantitative analysis will not be performed. In this case, a more detailed qualitative analysis by treatment group and / or visit could be provided.

4.7.1.2. Quantitative analysis

4.7.1.2.1. Values out of limits of detection

For quantitative description of concentration of these biomarkers, missing values with a result flag not equal to “In ranges” will be substituted as follows:

Value	Substituted by
Missing and below quantification limit (based on the result flag)	$LLOQ/\sqrt{2}$
Missing and above quantification limit (based on the result flag)	ULOQ

If the lower (respectively upper) limit of quantification is missing, then it is replaced by the lower (respectively upper) limit of detection in the substitution rules. Change from baseline and percentage of reduction from baseline to post-baseline time point will be calculated using imputed values at the visits.

4.7.1.2.2. Description of biomarkers concentrations by arm

For each treatment group (S95011 and placebo), descriptive statistics of biomarker concentration will be provided (in terms of value at each visit and relative change from baseline to each post-baseline visit) using descriptive tables.

4.7.2. Biomarker endpoints: Immune panel (C3 and C4 complement fractions, CH50 (or CH100), quantitative immunoglobulins, protein electrophoresis and immunofixation)

Immune panel is evaluated at W000, W004 and W013 in blood. In case of premature withdrawal, an evaluation is planned at this time-point and the evaluation will not be described in the following analysis.

Biomarker results will be described for patients of the Biomarker Set (BMKS).

For descriptive statistics, marker will be expressed in terms of concentration at baseline and at each post baseline visit and relative change from baseline to post baseline visit.

4.7.2.1. Description of biomarkers concentrations by arm

For each treatment group (S95011 and placebo), descriptive statistics of biomarker concentration will be provided (in terms of value at each visit and relative change from baseline to each post-baseline visit) using descriptive tables.

4.7.3. Biomarker endpoints: β 2 microglobulin

β 2 microglobulin is evaluated at W000, W004 and W013 in blood. In case of premature withdrawal, an evaluation is planned at this time-point and the evaluation will not be described in the following analysis.

Biomarker results will be described for patients of the Biomarker Set (BMKS).

For descriptive statistics, marker will be expressed in terms of concentration at baseline and at each post baseline visit and relative change from baseline to post baseline visit.

4.7.3.1. Description of biomarkers concentrations by arm

For each treatment group (S95011 and placebo), descriptive statistics of biomarker concentration will be provided (in terms of value at each visit and relative change from baseline to each post-baseline visit) using descriptive tables.

4.8. Pharmacokinetic analysis and PK/PD analysis

Serum concentrations of S95011 will be analysed by a population modelling approach, described in a separated Data Analysis Plan (DAP), in order to assess the pharmacokinetics of the drug and to investigate potential sources of variability through a covariate analysis. This analysis will provide pharmacokinetic parameters and their associated variability in patients and will be the object of a separate report.

Exploratory assessment of the relationship between exposure and pharmacodynamics (as safety and efficacy including biomarkers, efficacy and/or safety endpoints) will be performed and if applicable, population pharmacokinetic pharmacodynamic (PK/PD) models will be developed and a DAP will be set up and reported separately. Mechanistic model-based approaches (such as physiologically based pharmacokinetic (PBPK) modelling, quantitative systems pharmacology (QSP) modelling, etc.) may be used to better describe the PK and/or PK/PD of S 95011. Those models would be the object of separate reports and a dedicated DAP would be set for PBPK models.

All the above-mentioned analyses may require pooling data from CL2-95011-001 study with data from other clinical trials or from literature.

5. INTERIM ANALYSIS

Except for the blinded standard deviation reassessment, no interim analysis is planned. Moreover, the blinded standard deviation reassessment was not performed as the recruitment was not much longer than expected.

6. CHANGES TO PROTOCOL-PLANNED ANALYSES

The definition of the Randomised Set has been modified as the set of all included patients to whom a therapeutic unit (TU) was randomly assigned using IWRS. Indeed, a patient non included has been randomised by mistake. According to the ICH E9 addendum, the population has to be defined according to the clinical question of interest. So, it has been judged relevant to define the analysis population as above.

The definition of treatment groups has been modified as the treatment received at inclusion visit for all analysis sets. Indeed, a patient has been randomised to one treatment but received the other one at inclusion (forced allocation). Thus, this patient has continued taking treatment received instead of randomised treatment for the following dispensations and it has been judged relevant to define the treatment groups as above.

As a patient received an incorrect Therapeutic Unit (TU) at a post-W000 visit on the 13-week double-blind treatment period, this patient has potentially switched treatment group. Thus, it has been decided to complete the definition of treatment groups by precisizing that in such cases, the patient will be considered in the treatment group corresponding to their TU(s) received until the switch. The switch being considered as an intercurrent event, data recorded from the switch will be managed according to the considered estimand.

Since the final version of the protocol, a new score for assessment of Sjögren has been constructed. It has been considered relevant to add this new score (STAR) in the statistical analyses. Thus, a new objective and associated secondary analyses have been added in this SAP.

In the same line, the CRESS score (a score similar to STAR) has been considered relevant to evaluate the efficacy of S95011. Thus, a new objective and associated secondary analyses have been added in this SAP for this score.

As descriptive statistics has been considered sufficient to evaluate the efficacy of S95011 on the MFI, SF-36 and stimulated salivary flow, the estimands and associated inferential analyses has been deleted.

The BMK set has been added to the list of analysis sets in order to perform Biomarker exploratory analyses.

Regarding the estimand framework, some changes has been made between the protocol and the SAP on intercurrent events. Indeed, “*study drug discontinuation for major worsening of primary Sjögren’s syndrome or AE related to study drug*” has been split into two independent IEs as “*study drug discontinuation for major worsening of primary Sjögren’s syndrome*” (IE1) is considered more impacting than “*Study drug discontinuation for AE related to study drug*” (IE3). Thus, for sensitivity analyses, it is has been decided to handle data post the IE1 using a reference based multiple imputation (“jump to placebo” approach) while data post the IE3 are considered moderately bad outcome and will be handled using a reference based multiple imputation (“copy increment in reference” approach). In the same line, intercurrent event “*change or initiation of unauthorised medication*” from the protocol has been split into “*Increase or initiation of authorized medication for pSS*”(IE2) and “*Decrease or stop of authorized medication for pSS*” (IE6) (the unauthorized part being necessarily linked to discontinuation for major worsening this part is already handled by IE1). Here again, IE2 having more impact than IE6, post IE data will be handled using different method (respectively reference based multiple imputation “copy increment in reference” and MAR approaches) for sensitivity analyses. Finally, IE5 “*Switch of treatment group (error of dispensation)*” has been added to handle the case of the patient having a treatment switch discussed above (MAR approach).

For all efficacy analyses, it has been specified that if the regression or the imputation model does not run due to too few patients in the stratas, the four classes randomisation stratification factor will be replaced by a 2 classes composite factor: baseline intake of oral corticosteroids or antimalarial or both (yes/no). If the model is still not running, then the stratification factor will not be considered.

Finally, for the treatment policy efficacy analysis, it has been considered sufficient to consider only responders in ESSDAI defined as patients with an improvement of at least 3 points and responders in ESSPRI defined as patients with an improvement of at least 1 point.

The salivary gland tissue will not be described because of the very small number of available biopsies collected at W013.

Due to very low number of viable cells collected at each time point, no statistical analysis will be performed on PBMCs (cell subsets).

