4.3. Study products and blinding systems

4.3.1. Products administered (IMP)

S95011 will be manufactured by OSE (Nantes, France) and placebo by Les Laboratoires Servier Industrie (Gidy, France).

Les Laboratoires Servier Industrie (Gidy, France) will pack, release and supply the therapeutic units (TUs) of S95011/Placebo.

During the screening period (from ASSE to W000), no treatment will be dispensed.

During the treatment period (from W000 to W013):

- S95011 or placebo will be dispensed for a double-blind period, from W000 to W010.

During the follow up period, no treatment will be dispensed.

Table (4.3.1) 1 provides a description of the IMP (S95011/Placebo)

Table (4.3.1) 1 - Description of the IMPs

	IMP	
	S95011	Placebo
Pharmaceutical form	Concentrate for solution for infusion	Concentrate for solution for infusion
Unit dosage	50mg/mL	NA
Appearance	A colorless to slightly yellow, clear to slightly opalescent aqueous solution	A colorless to slightly yellow, clear to slightly opalescent aqueous solution
Composition	Histidine acetate, sorbitol, glycine, polysorbate 20, anti-CD127 mAb and water for injection	Histidine acetate, sorbitol, glycine, polysorbate 20 and water for injection

Table (4.3.1) 2 provides a description of the packaging of the IMP(s).

Table (4.3.1) 2 - Description of packaging

Number of units of the pharmaceutical form per primary packaging	A vial of 2 mL of S95011 concentrate for solution at 50mg/mL or placebo
Number of primary packaging per secondary packaging	1 vial per box
Number of secondary packaging per patient	9 boxes per visit

The labelling of packages complies with the regulatory requirements of each country involved in the study.

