5.6. Patient withdrawal**5.6.1. Withdrawal criteria**

Study drug dose adjustments and/or interruptions are not allowed in this study. However, in case of delay in dosing administration for any reason (*e.g.* AE,...), continuation of IMP should be discussed and agreed with the sponsor.

Patients may voluntarily discontinue the study for any reason at any time.

The Investigator should discontinue IMP for a given patient if, on balance, he/she believes that continuation would be detrimental to the patient's well-being.

The reasons for premature discontinuation of IMP are:

- **Adverse events** according to the judgement of the investigator or according to the following predefined criteria:
 - Any adverse event \geq Grade 3 (according to [CTCAE/v5.0](#) grading) considered as related to the IMP administration,
 - Study treatment related cytokine release syndrome of grade 2 or higher ([CTCAE v5.0](#) grading),
 - Major worsening of primary Sjögren's syndrome as judged by the Investigator.
- Pregnancy of the patient,
- Major deviation to protocol if it jeopardises patient's safety, e.g. any medical event requiring administration of an unauthorised concomitant treatment (see [Section 6.3](#)).
- Non-medical reason (to be carefully described) e.g. consent withdrawal, patient's removal.

Patients who discontinue study treatment should not be considered withdrawn from the study unless they withdraw their consent. They will perform a withdrawal visit (with all investigations described at W013 visit) and two FU visits, 9 and 18 weeks after the last IMP administration (see investigations in the investigational schedule table).

Information to be collected during the last visit of these patients is given in [Section 5.6.2](#). These follow-up modalities are used to ensure the efficacy and safety evaluation of all patients who received the IMP.

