6.2. IMPs dispensing

The treatment group will be allocated *via* IWRS using a central randomisation (2:1) to S95011 or placebo with stratification by baseline intake of oral corticosteroids (yes/no) and baseline intake of antimalarial (*e.g.* chloroquine, hydroxychloroquine, quinacrine) (yes/no).

At inclusion visit (W000), patient will be randomised to S95011 or placebo by IWRS. A connection to the IWRS should be performed at each concerned visit (from W000 to W010) to know the allocated kit numbers to be used for the infusion bag preparation (see details in IWRS manual).

Therapeutic units will be identified by a 6-digit number for identification, tracking and stock management purposes. For each administration, 9 vials of IMP will be delivered.

The detachable portion of the label on the IMP box must be stuck by the investigator's staff on the prescription form when the IMPs are dispensed by a pharmacist.

For each patient, the IMP will only be dispensed during the study. At W010 visit, the last administration of the IMP will be performed.

At last study visit, the investigator will propose a treatment adapted to the nature of the clinical state of the patient.

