The salivary stimulants (e.g. cevimeline, pilocarpine), cyclosporine eye drops and lifitegrast should not be used during the **12 hours prior to**, and during the assessment of clinical disease outcome measurements (Schirmer test and sialometry). Artificial tears and artificial saliva should not be used during the **4 hours prior to**, or during the assessment of clinical disease outcome measurements (Schirmer test and sialometry).

Prohibited Concomitant Medications

Patients are not permitted to receive any of the following immunosuppressants or biological therapy (monoclonal antibodies, fusion proteins) while receiving IMP. These treatments act as S95011 on the immune system and the safety profile of such combinations are not yet known. Duration of wash out periods depends on half lives of products and immune system recovery.

- Corticoids greater than 10mg/day prednisone or equivalent
- Methotrexate > 25 mg/week
- Belimumab
- Rituximab
- Abatacept
- Tumor necrosis factor inhibitors (adalimumab, certolizumab, etanercept, golimumab, infliximab and biosimilars)
- Tocilizumab
- Cyclophosphamide (or any other alkylating agent),
- cyclosporine (except for eye drops), tacrolimus, sirolimus, mycophenolate mofetil, azathioprine, or leflunomide
- JAK inhibitors

Furthermore, any live or attenuated vaccine are forbidden. Administration of recombinant or killed virus or messenger RNA or replication-incompetent vector vaccines, including SARS-CoV-2 vaccines, are acceptable. Vaccination of patients during treatment with S95011 and prior to clearance of S95011 is likely to result in non-protective antibody titers due to the pharmacologic activity of S95011. Consequently, all vaccinations deemed necessary by the investigator for the patient should be up to date before inclusion.

If the patient needs to receive one of these prohibited medications, she/he will have to discontinue the investigational product and will perform a withdrawal visit (with all investigations described at W013 visit) and two FU visits, 9 and 18 weeks after the last IMP administration (see investigations in the investigational schedule table).

A list of the above prohibited and unauthorized treatments **by drug class** can be consulted in the e-CRF.

Rescue treatment

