10.1.2.4. Efficacy analysis

10.1.2.4.1. Primary estimand based on the ESSDAI

The primary estimand of interest is the effect of the initially randomised treatments on the clinical disease activity in all patients assuming non-occurrence of intercurrent events. The motivation for this choice is to assess at this proof-of-concept stage the full efficacy potential, that is, the pharmacologic effect of the S95011 if all patients adhere to it (without any intercurrent events).

The attributes of the primary estimand are defined as follow:

- Treatment: S95011 or placebo
- Population: RS
- Variable: change in ESSDAI total score from baseline to W13 (primary efficacy endpoint).
- Summary measure: difference in means between treatments.
- Intercurrent events (IE):
 - change or initiation of unauthorised medication
 - study drug discontinuation for major worsening of primary Sjögren's syndrome or AE related to study drug
 - study drug discontinuation for other reasons (non-medical reason, AE not-related...)
 - unexpected others events having a major impact on the pharmacologic effect evaluation (They will be defined at the latest in the final version of the SAP).

The rate of IEs is assumed to be below 10%. They will be handled by a hypothetical strategy to estimate what the outcome would have been at the designated time point if no IE would have occurred through that time point, considering that patients with IE would have efficacy outcomes as patients, in their treatment group, who continue their randomised treatment without IE.

10.1.2.4.1.1. Primary analysis

The primary analysis for the primary estimand will be conducted using only data obtained prior to IEs. Values post IE will not be taken into account and will be imputed according to the MAR assumption (multiple imputation by treatment group). This is aligned with the primary estimand and the hypothetical strategy.

S95011 will be compared to placebo on the primary efficacy endpoint in the RS, using a General Linear Model including the fixed, categorical effect of treatment and randomisation stratification factors (*rando_factor*) as well as the continuous fixed covariate of baseline value.

GENERAL LINEAR MODEL: change = baseline rando_factors treatment

The assumptions underlying the model, as for instance, the normality and homoscedasticity of residuals and detection of outliers, will be checked.

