Missing data (not linked to intercurrent events) will be imputed according to the MAR assumption with a multiple imputation by treatment group.

The hypotheses to be tested are:

Let μ_0 and μ_1 be the population means of the change from baseline in ESSDAI score at W13 (primary endpoint) under placebo and S95011, respectively. The statistical hypotheses that will be tested are:

$$H_0: \mu_0 \geq \mu_1 \text{ (S95011 is not superior to placebo)}$$

versus

$$H_1: \mu_0 < \mu_1 \text{ (S95011 is superior to placebo)}$$

The type I error of the statistical tests will be set at 10% for unilateral situation, which is consistent with the objective of demonstrating the superiority versus placebo.

The following elements will be provided in a summary table:

- Estimate (standard error) of the difference between adjusted treatment group means.
- Two-sided 80% CI of the estimate
- Two-sided 95% CI of the estimate.
- One-sided p-value

10.1.2.4.1.2. Sensitivity analyses

In order to assess the sensitivity to the missing at random (MAR) assumption, values post the following IEs:

- change or initiation of unauthorised medication,
- study drug discontinuation for major worsening of primary Sjögren's syndrome or AE related to study drug,

will not be taken into account and will be imputed according to the missing not at random (MNAR) assumption. The values of outcome will be imputed using a reference based multiple imputation ("copy increments in placebo" approach) for S95011 group and using multiple imputation for the placebo group. This approach assumes that patients from S95011 will exhibit an evolution of the disease similar to patients in the placebo group but starting from the benefit already obtained (Carpenter *et al*, 2013). The imputed value will reflect the fact that these IEs are considered a moderately bad outcome. The others IEs and missing data will be handled as in the primary analysis.

10.1.2.4.1.3. Supplementary analyses

Responders ESSDAI at W13 defined as patients having improvement from baseline in ESSDAI total score of at least:

- 3 points
- 5 points
- 7 points

will be analysed separately using a logistic regression model including the fixed, categorical effect of treatment and randomisation stratification factors (*rando_factor*) as well as the continuous fixed covariate of baseline value. The handling of IEs and missing data will be the same as the primary and sensitivity analysis.

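### SAP 6 drops the protocol's separate event for unauthorised medication as already covered by IE1, yet a prohibited drug taken while infusions continue meets no intercurrent event

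*SAP*

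**What the plan says.** Protocol 10.1.2.4.1 lists "change or initiation of unauthorised medication" as an intercurrent event, separate from the two study-drug-discontinuation events. In the protocol's sensitivity analysis, values after that event "will not be taken into account and will be imputed according to the missing not at random (MNAR) assumption", by copy increments in placebo for S95011.

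SAP 6 replaces it with IE2 (increase or initiation) and IE6 (decrease or stop), both restricted to authorised pSS medication. It explains the omission in these words: "the unauthorized part being necessarily linked to discontinuation for major worsening this part is already handled by IE1".

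SAP 7.2.2.1 defines IE1 as a pSS-related adverse event leading to study drug discontinuation, IE3 as an IMP-related adverse event leading to discontinuation, and IE4 as a missed infusion with all later ones missed. Under SAP 4.3.1.1 the primary analysis uses only data obtained before an intercurrent event.

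On prohibited drugs, Protocol 6.3 says: "Patients are not permitted to receive any of the following immunosuppressants or biological therapy (monoclonal antibodies, fusion proteins) while receiving IMP". A patient who needs one is told that "she/he will have to discontinue the investigational product". On timing, Protocol 6.2 says: "At W010 visit, the last administration of the IMP will be performed". The primary endpoint is at W013.

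**The concern.** The primary estimand asks what the outcome would have been had no intercurrent event occurred. That works only if each relevant event is flagged. If a prohibited immunosuppressant or biologic raises no flag, the W013 ESSDAI stays in as observed and any effect of that drug is credited to the randomised comparison. The sensitivity analysis relies on the same flags, so it cannot reveal the problem. With 15 placebo patients and a success rule that turns on an estimated difference of at least 3 points, a single patient carries visible weight.

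**Working it through.** **Is the link necessary?** Protocol 5.6.1 puts major worsening among the adverse-event reasons for stopping IMP. It puts "any medical event requiring administration of an unauthorised concomitant treatment" under a different reason, major deviation. The stopping rule in Protocol 6.3 carries no condition on indication. SAP 4.1.2 keeps deviation categories both for forbidden concomitant treatment and for patients who met withdrawal criteria but were not withdrawn, so the SAP itself foresees prohibited use without discontinuation. The link is therefore not necessary.

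**Does any event catch these cases?** A is a prohibited biologic, alkylating agent, JAK inhibitor or non-methotrexate immunosuppressant taken while infusions continue. B is a corticosteroid dose above the protocol limit (10 mg/day prednisone or equivalent), started more than 4 weeks before W013 and held unchanged, with IMP continued. C is a drug of the type in A started after the W010 infusion.

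| Event | A | B | C |
|---|---|---|---|
| IE1, IE3 | No: IMP not stopped | No: IMP not stopped | Only if an AE is recorded as leading to discontinuation after the last infusion |
| IE2 | No: classes absent from its seven code lists, judged by title | No: start is outside the 4-week window and dose level is not tested | No: same lists |
| IE4 | No | No | No: no infusion left to miss |
| IE5 | No | No | No |
| IE6 | No | No, unless reduced or stopped in the window | No |

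Eight code lists covering the classes in A and C already exist in SAP 7.2.1.1.4, but only for previous treatments.

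Some cases are caught and are not part of this point. IE2 covers any methotrexate initiation or increase after W000, and corticosteroid starts, increases or injections in the last 4 weeks. Patients who stop IMP before W010 fall under IE1, IE3 or IE4. A corticosteroid course that ended before the window matches the trial's own entry wash-out in exclusion criterion 31.

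**Reproducing the plan's figures.** Inputs from Protocol 10.2 and SAP 1.2: 30 and 15 patients, SD 6, one-sided 10% test, and an estimated difference of at least 3 points.

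- SE = 6 × √(1/30 + 1/15) = 1.897.
- Critical difference = 1.2816 × 1.897 = 2.43 (2.47 with t on 43 df). This is below 3, so the 3-point criterion governs.
- P(success) = 1 − Φ((3 − d)/1.897): 70.1% at d = 4, 50.0% at d = 3, 5.7% at d = 0. The plan states about 70%, 50% and 5%.

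**Illustration.** One patient and an extra ESSDAI fall of r points are assumptions, not figures from the documents.

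- Placebo patient, true difference 4: d = 4 − r/15. At r = 3, d = 3.80 and P = 66.3%. At r = 7, d = 3.53 and P = 61.1%.
- S95011 patient, true difference 0: d = r/30. At r = 3, d = 0.10 and P = 6.3%. At r = 7, d = 0.23 and P = 7.2%.
- With SD 4, the low end of the range the plan cites, SE = 1.265. For r from 0 to 7, success goes from 79% to 66% and false positives from 0.9% to 1.4%.

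**The case against.** Cases A and B require two breaches: a prohibited drug or dose is taken, and the mandatory stop is ignored. Both would be reported as important deviations. That makes them rare, but reporting a deviation does not remove the value from the estimate.

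A reader might infer that every prohibited drug started after W010 escapes all events. The documents do not support that. Only IE4 is defined by a missed infusion. SAP 7.2.3.1 counts actions taken up to the end of the studied period, and Protocol 4.3.1 runs the treatment period to W013. An investigator might therefore record a discontinuation for an adverse event after W010, and IE1 or IE3 would then apply. The SAP does not settle this, so case C is a possible gap.

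A reader might also infer that such use would be hidden. It would not. SAP 4.2.2 tabulates all concomitant treatments by ATC code, preferred name and arm, and SAP 4.1.2 reports deviations by period. The remaining limit is that SAP 7.2.1.3 pools starts after the last infusion with those in follow-up.

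Nor do the documents show a changed sensitivity imputation for patients who did stop IMP because of a prohibited drug. Under the protocol they could fall under more than one event, and it gives no order of precedence.

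Finally, Protocol 6.3 words the ban as applying while IMP is received. On that reading a start after W010 is not unauthorised, and the protocol's own event would not have caught it either. This stands as a reason to reconcile the passages first. It does not touch cases A and B.

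**Conclusion.** The stated reason for dropping the event is wrong on the documents' own text. Cases A and B meet no intercurrent event, and case C may meet none. In those cases the W013 value is used as observed in both the primary and sensitivity analyses, contrary to the hypothetical estimand. The treatment-policy estimand is unaffected.

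The conclusion rests on code lists judged by title, since the files themselves are not in the documents. It does not show that the trial's result is biased, because no such patient is documented. For case C at most about 21 days separate drug start from W013, while Protocol 2 expects the selected domains to change within 3 months, so the effect may be near zero. The illustrative cost is roughly 4 to 9 percentage points of success for one placebo patient, or 0.6 to 1.5 points of false-positive rate for one S95011 patient, at assumed falls of 3 to 7 points. The definition should be corrected: the defect lies in the primary analysis and the remedy is cheap.

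**What to change.** - Correct the sentence in SAP 6.
- Restore an intercurrent event for starting a protocol-prohibited immunosuppressant or biologic, dated at drug start and independent of IMP discontinuation. Code it with the lists in SAP 7.2.1.1.4 (1728.2, 3432.1, 4299.0, 4300.0, 4303.0, 4305.0, 4308.0, 4618.0), limited to what Protocol 6.3 prohibits, so that permitted cyclosporine eye drops, for example, are excluded.
- Add to IE2 a check for a corticosteroid dose above the protocol's own limit within the existing 4-week window.
- Set later values to missing in the primary analysis. In the sensitivity analysis use the protocol's copy increments in placebo, with MAR for placebo patients. State the event's place in the order, for example next to IE2.
- Reconcile Protocol 6.3, 4.3.1 and 10.1.2.4.1 to decide whether the event runs to W010 or to W013, and state whether IE1 and IE3 can occur after the last infusion.

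The cost is SAP wording, one flag and one dose check from medication data already collected, and possibly a few more imputed values. There is a real trade-off for starts after W010: the discarded W013 value would be imputed from W004, the only other post-baseline ESSDAI. This is an analysis flag and changes no patient management.
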